### **6.2.2 Enrollment, Baseline, and/or Randomization**

#### **Enrollment**

Enrollment and randomization. Patients will be contacted, screened, enrolled, and randomized in the same way whether they are self-referred (i.e., opt out letters, toll free phone number) or provider referred. After receiving a provider or patient referral, VA Connecticut study staff will contact patients by telephone, and using a semi-structured interview, assess patient interest, patient's self-reported ability to walk at least one block, presence of a landline or cellular telephone, and absence of vision or hearing loss that would interfere with participation (to confirm eligibility criteria not reliably contained in the EHR) and answer any questions patients have about the intervention (see attached script) as well as review their VA medical record to confirm eligibility. If a patient is willing to obtain treatment, study staff will read the approved consent language contained in the information sheet and will set up the patient to receive a baseline telephone assessment. Next, after baseline completion, study staff will randomize the patient. Patients who are randomized to CBT-CP will be referred to a site CBT-CP clinician by study staff using the preferred local method.

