*Substance Use Diagnosis.* We will abstract from each participant's VA electronic health record current (in the past 12 months) and past diagnosis of alcohol use disorder (diagnosis prior to the past 12 months).

*Synchronous treatment characteristics.* A trained research assistant will review each participant's electronic medical record at the completion of treatment to collect treatment characteristics, (platform, mode), time to treatment, treatment dose, time to completion, completion (y/n), and treatment quality.

IVR-collected outcome data. In addition to passively collected EHR data, we will actively collect patient-reported outcome data using automated IVR calls at baseline, 1, 4, 6, and 12 months. COPEs patients will receive regular IVR assessments as part of the COPEs intervention. At the baseline and follow-up periods they will be asked to complete the outcomes assessment at the end of a regularly scheduled call. CBT-CP patients will be enrolled in the IVR system after randomization and scheduled for assessment calls at baseline, 1, 4, 6, and 12 months. They will be informed of the 5-10 minute automated telephone interview to assess their pain and physical and emotional functioning, sleep, and satisfaction with their pain care at baseline and in 1, 4, 6 and 12 months. All measures demonstrate strong psychometric properties. IVR assessment allows us to collect outcomes data in a pragmatic, low burden manner, with no need for an in-person visit. We will not reimburse participants for cellphone minutes.

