## **Randomization**

Randomization Participants will be randomized in a 1:1 ratio to one of the two treatments (COPEs or synchronous CBT-CP). The randomization sequence will be generated by the study statistician using statistical software and concealed in the study database until the time of randomization. We will randomize participants during the enrollment call. Randomization will be stratified by site and gender and will be done according to a permuted block design with variable block size (4 and 6) in order to maintain balanced treatment assignment.

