## **9.2 Sample Size and Randomization**

Assuming a standard deviation of BPI interference of 2.4 (as observed in a previous study (SCOPE)), a total sample size of 610 subjects (305 per group) would provide 80% power to detect a mean difference in BPI interference of 0.55 between groups at 4 months using a two-sided t-test at significance level  $\alpha=0.05$ , and 90% power to detect a difference of 0.63. To account for an expected attrition rate of 20%, we will enroll a total of 764 participants (382 per group). Half of the participants will be female.

Although the randomization will be done at the patient level, there may be some clustering due to the therapist delivering the intervention. We conducted a simulation study to investigate the effect of this clustering on power. We assumed that in the COPEs arm (treatment delivered remotely by IVR) 9 therapists will be delivering the intervention (each to an equal number of subjects), and in the synchronous CBT arm 38 therapists will be delivering the intervention. Based on a prior pain trial of group cognitive behavioral treatments, we used an estimate of therapist-level intracluster correlation coefficient (ICC) of 0.01. Simulations (N=100000) showed that we will

have at least 84% power to detect a difference in BPI of 0.65 with an ICC of 0.01 or less using a mixed model on the outcome at 4 months with a therapist random effect.

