## **9.6 Data Analyses**

Quantitative Analysis. As an estimate of uptake, we will present the proportion of patients who agree to be randomized out of all who are offered referral to treatment in our study. Randomization success will be assessed by side-by-side summaries of

baseline demographic and clinical characteristics of subjects by treatment group. Analyses of all outcomes will be done according to the intent-to-treat principle.

Primary Analysis. We will test and estimate the difference between COPES and CBT-CP in terms of BPI interference by using a linear mixed-effects model which simultaneously models all available BPI interference measurements including baseline. The model will contain fixed effects for treatment (categorical: COPES vs. CBT-CP), site (categorical), gender (categorical), time (categorical: baseline, 1, 4, 6, 12 months), and the treatment-by-time interaction. The only covariates that will be included in the primary and secondary analysis (including subgroup analyses) are site and gender. We are adjusting for these 2 variables because they are used for stratification in randomization. An unstructured variance-covariance matrix will be used to model correlations among repeated measures within a subject, and a therapist random effect will be used to model the correlation of outcomes in subjects who share the same therapist. Because this is a randomized trial, in the model above we will impose the constraint that the means for the two groups are equal at baseline (that is, we will perform a constrained longitudinal data analysis). Following the CONSORT recommendations, we will not perform any test for baseline differences as these tests are not needed in a randomized clinical trial “Such significance tests assess the probability that observed baseline differences could have occurred by chance; however, we know that any differences are caused by chance” This model will allow us not only to assess the between-group difference at 4 months (primary endpoint), but also to evaluate in secondary analyses whether between-group differences are maintained over time (at 6 and 12 months). Results will be summarized as least-squares means (and their 95% confidence interval) within and between groups. The primary analysis will be conducted at significance level 0.05.

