### **11.2 Informed Consent Forms**

Patients will be contacted, screened, enrolled, and randomized in the same way whether they are self-referred or provider referred. After receiving an electronic referral from a clinician at a study site or a voicemail from a patient self-referral, VA Connecticut study staff will contact patients by telephone, and using a semi-structured interview, assess patient interest, patient's self-reported ability to walk at least one block, presence of a landline or cellular telephone, and absence of vision or hearing loss that would interfere with participation (to confirm eligibility criteria not reliably contained in the EHR) and answer any questions patients have about the intervention (see attached script) as well as review their VA medical record to confirm eligibility. If a patient is willing to obtain treatment, study staff will read the approved consent language contained in the information sheet and will randomize the patient. Patients will be specifically asked about consenting to the audio recording of their voice. We will record the patients' confirmation of this consent. The information sheet will be available to patients on our study website. The website is a resource for patients and has copies of the information sheet, the patient handbook and audio files of the relaxation exercises. Patients do

not need to login and it does not collect, hold or request any PHI or patient data. Use of the website will allow patients to view a copy of the information sheet without the delay of prior mailing. If patients do not have access to the internet or if they would prefer a physical copy prior to consenting, we will mail them a copy and contact them at a later time for consenting.

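### The protocol gives two orders for baseline BPI interference and randomisation; if baseline comes second, equal baseline means are not guaranteed and the primary estimate could be biased in either direction

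*Combined protocol and SAP*

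**What the plan says.** **Baseline first.** Section 4.3 enrols all consenting patients in the IVR system so that baseline can be obtained, and randomises them once it is complete. Section 6.2.2 (Enrollment) agrees: "Next, after baseline completion, study staff will randomize the patient". Section 9.2 (Treatment Assignment Procedures) makes a completed baseline survey a condition of randomisation.

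**Randomisation first.** Section 6.2.2 (Baseline Assessments, IVR-collected outcome data) states: "CBT-CP patients will be enrolled in the IVR system after randomization and scheduled for assessment calls at baseline, 1, 4, 6, and 12 months". The same paragraph has COPES patients complete the baseline outcomes assessment at the end of one of their regular COPES calls. The Précis (Design and Outcomes) and section 3 describe the pre-treatment assessment as something asked of all randomised patients.

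**Unclear.** Section 6.2.2 (Randomization) says "We will randomize participants during the enrollment call". Section 11.2 has staff read the consent language "contained in the information sheet and will randomize the patient", with no baseline step between.

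**Analysis.** Sections 9.3 and 9.6 fit a constrained longitudinal model. Section 9.6 will "impose the constraint that the means for the two groups are equal at baseline" and justifies this by randomisation. The first sensitivity analysis in 9.6 is an ANCOVA of the 4-month score that adjusts for baseline BPI interference. Section 6.2.3 says patients are not blinded. No section says how a baseline recorded after randomisation is to be handled.

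**The concern.** Randomisation makes expected group means equal only for values that allocation cannot have affected. BPI interference is self-reported. A patient who already knows which form of CBT they will receive may answer differently, and section 6.2.2 describes different baseline calls for the two arms. Selective completion of a post-allocation baseline could have the same effect. Any resulting baseline difference is treated by the constrained model as chance imbalance and adjusted for, which moves the 4-month contrast. The planned ANCOVA makes the same adjustment, so agreement between the two analyses would not reveal the problem. The primary comparison is at stake.

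**Working it through.** **1. Can the statements be reconciled?**
- Section 4.3 enrols everyone in the IVR system before randomisation; the 6.2.2 paragraph enrols control patients after it. Both cannot be true.
- The COPES half of that paragraph also conflicts with the Précis and section 5.1, which start the daily COPES calls only after the study baseline evaluation. On that account there is no regular COPES call on which to take baseline.
- The enrolment-call sentence in 6.2.2 and the consent text in 11.2 omit or blur the baseline step. Neither says that baseline follows randomisation.

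**2. The plan's own figures.** Inputs from section 9.2: "Assuming a standard deviation of BPI interference of 2.4"; an evaluable size of 305 in each arm; and the claim that this number "would provide 80% power to detect a mean difference in BPI interference of 0.55 between groups at 4 months using a two-sided t-test". From section 9.6: "The primary analysis will be conducted at significance level 0.05".
- n per arm = 2 × (1.96 + 0.84)² × (2.4/0.55)² ≈ 299, or 598 in total, against the stated 610.
- Power with 305 per arm is 0.81 at 0.55 and 0.90 at 0.63.
- 305/0.8 = 381.25, rounded up to 382 per arm, 764 in total.

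The stated figures reproduce.

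**3. Bias formula.** Let d₀ be the COPES-minus-control difference in mean baseline caused by allocation, and ρ the within-arm correlation of baseline with the 4-month score. With complete data and equal SDs, the constrained model gives the ANCOVA estimate, so

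expected estimate = true effect − ρ·d₀.

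The standard error is 2.4 × √(2/305) × √(1 − ρ²). Neither ρ nor d₀ is in the documents. The assumed ranges are ρ from 0.3 to 0.7 and d₀ from 0 to 0.5 points in size. Therapist clustering and missing data are left out.

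| ρ | SE | Bias (type I error), shift 0 | Shift 0.1 | Shift 0.2 | Shift 0.5 |
|---|---|---|---|---|---|
| 0.3 | 0.185 | 0 (0.050) | 0.03 (0.053) | 0.06 (0.062) | 0.15 (0.128) |
| 0.5 | 0.168 | 0 (0.050) | 0.05 (0.060) | 0.10 (0.091) | 0.25 (0.318) |
| 0.7 | 0.139 | 0 (0.050) | 0.07 (0.080) | 0.14 (0.172) | 0.35 (0.713) |

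At a shift of 0.2 the bias is 0.06/0.55 = 11% to 0.14/0.55 = 25% of the design difference.

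**4. Simulation check.** The five-time-point constrained model with unstructured covariance was run 600 times per setting, with 305 per arm and a true effect of −0.55.
- No baseline shift: −0.551, −0.553 and −0.559 for ρ = 0.3, 0.5 and 0.7.
- COPES baseline 0.2 lower: −0.483, −0.444 and −0.420. The formula gives −0.49, −0.45 and −0.41.
- COPES baseline 0.5 lower: −0.398, −0.290 and −0.199. The formula gives −0.40, −0.30 and −0.20.

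The ANCOVA gave the same values as the constrained model. The unadjusted 4-month difference stayed between −0.540 and −0.557.

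**5. Direction.** A lower COPES baseline pulls the estimate toward no benefit. A higher one exaggerates the benefit.

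**The case against.** The strongest reply is that the sections governing enrolment and treatment assignment (4.3, 6.2.2 Enrollment, 9.2) are explicit and agree. Section 9.3 also describes the least-observed patients as having only a baseline, which presupposes that everyone randomised has one. On this view the IVR paragraph is leftover text. The COPES text also uses the word baseline for a separate seven-day run-in that serves treatment.

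Much of this stands: the weight of the text favours baseline first, and the consent section and the enrolment-call sentence are omissions or loose wording rather than direct contradictions. But the IVR paragraph is the operative description of how outcomes are collected. It refers to the outcomes assessment, not the run-in, and the Précis and section 3 fit it.

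A reader might go further and infer that a post-randomisation baseline makes the constraint invalid and the estimate biased. The documents do not support that. If the baseline is taken before treatment and nothing about allocation moves the answers, the means are still equal in expectation and there is no bias. Both arms receive active CBT, so the shift from merely learning the allocation may be small; the documents give no information on it. Nor would a randomised patient with no baseline be lost, because the constrained model keeps that patient through follow-up scores.

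**Conclusion.** The contradiction is real and bears on the primary analysis. The consequence is conditional. If baseline was taken after unblinded randomisation, equal means are no longer guaranteed, and both baseline-adjusted analyses could be off by about ρ times any induced difference, with either sign. That is zero without a shift, and 0.06 to 0.14 points for an assumed shift of 0.2 and ρ of 0.3 to 0.7. These figures illustrate sensitivity; they are not estimates of what happened. They assume complete data, equal SDs, no therapist clustering, and a shift that affects baseline but not the 4-month score. It would be wrong to infer that baselines were in fact collected late: the documents cannot settle that, but time stamps can. The point should be corrected because the plan as written permits the problem and has no rule for it.

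**What to change.** 1. Rewrite the IVR paragraph in section 6.2.2 to the order in 4.3, 6.2.2 (Enrollment) and 9.2: consent, IVR enrolment of all patients, baseline survey, then randomisation. Remove the arm-specific baseline procedures. Clarify the Précis, section 3, 6.2.2 (Randomization) and 11.2 to match.
2. Compare the IVR and randomisation time stamps and report, by arm, how many baseline scores were recorded after randomisation. This works even if enrolment has closed, provided both events are time-stamped.
3. Add to section 9.6 a sensitivity analysis that refits the primary model with any post-randomisation baseline values set to missing. The patients stay in the analysis through their follow-up scores.

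The cost is wording in five places, one date comparison and one sentence in 9.6, with no new data collection. Locking the randomisation module until baseline is complete is optional, would need system work, and helps only while patients are still being enrolled.

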## **Randomization**

Randomization Participants will be randomized in a 1:1 ratio to one of the two treatments (COPEs or synchronous CBT-CP). The randomization sequence will be generated by the study statistician using statistical software and concealed in the study database until the time of randomization. We will randomize participants during the enrollment call. Randomization will be stratified by site and gender and will be done according to a permuted block design with variable block size (4 and 6) in order to maintain balanced treatment assignment.

### **6.2.3 Blinding**

IVR assessment calls are automated so all data collection is blinded. Due to the nature of behavioral interventions, neither patient or provider will be blinded to their treatment condition. The statistician will be blinded. An independent statistician will create the randomization allocation schedule and this schedule will be incorporated into the IVR system so that it will remain masked. We will work with the Yale Center for Analytical Sciences to obtain statistical support for the DSMB report preparation and meetings and other tasks that will involve unblinded data. This will allow us to have a blinded statistician.

### **6.2.4 Follow up Visits**

Follow-up information will be collected by the IVR system; there will be no in-person visits. With the exception of demographic data and treatment satisfaction, outcomes and covariates described in the baseline will be assessed at 1, 4, 6, and 12 months post-baseline. The four-month outcome will be the primary outcome. Follow-up assessments may be collected anytime within the window of 1 week prior to the planned assessment date to one month after. In order to minimize missing data, when participant do not complete the planned IVR assessment we will attempt to collect the information using telephone interview or survey mailing to the participant's home.

Various domains of pain treatment satisfaction will be assessed using a subscale of the Patient Outcomes Questionnaire at the four month outcome timepoint. This 5-item measure shows good internal consistency and significant associations with staff and patient ratings of patient improvement.

### 6.2.5 Completion/Final Evaluation

The final visit will be the same as the follow up visits listed above.

## 7. SAFETY ASSESSMENTS

Study progress and safety will be reviewed monthly. Progress reports, including patient recruitment, retention/attrition, and adverse events (AEs) will be provided to the Independent Monitor(s) semi-annually. An Annual Report will be compiled and will include a list and summary of AEs. In addition, the Annual Report will address (1) whether AE rates are consistent with pre-study assumptions; (2) reason for dropouts from the study; (3) whether all participants met entry criteria; (4) whether continuation of the study is justified on the basis that additional data are needed to accomplish the stated aims of the study; and (5) conditions whereby the study might be terminated prematurely. The Annual Report will be sent to the Independent Monitor(s) and will be forwarded to the IRB and NCCIH. The IRB and other applicable recipients will review progress of this study on an annual basis. The IRB and NCCIH Program Officials will receive copies of all study monitoring/audit or inspection reports within 14 day of PI receipt.

Table of reporting activities

Data type	Frequency of review	Reviewer
Subject accrual (including compliance with protocol enrollment criteria)	Monthly	PI, Internal QA Reviewer
	Semi-annually	Independent Monitor(s)
Status of all enrolled subjects, as of date of reporting	Monthly	PI, Internal QA Reviewer
	Semi-annually	Independent Monitor(s)
Data entry quality control checks on 10% of charts	Weekly	QA Reviewer
Adherence data regarding study visits and intervention	A monthly report will be prepared containing information on those assessed.  Participants will be assessed at the end of treatment and subsequent assessment points	PI, Internal QA Reviewer
	Semi-annually	Independent Monitor(s)
AEs and rates	A monthly report will be prepared containing	PI, Internal QA Reviewer

	information on those assessed. Participants will be assessed at the end of treatment and subsequent assessment points	
	Semi-annually	Independent Monitor(s)
	Annually	NCCIH, FDA (If Applicable)
SAEs (unexpected and related)	Per occurrence	PI, Independent Monitor (s) NIH/NCCIH, FDA (if applicable)
SAEs (expected or unrelated)	Per Occurrence	PI, Internal QA Reviewer
	Annually	Independent Monitor (s), NIH/NCCIH
Unanticipated Problems	Monthly	PI, Internal QA Reviewer
	Per Policy	IRB, FDA (if applicable)

## 7.1 Specification of Safety Parameters

The interventions are minimal risk and in fact are two forms of guideline recommended non-pharmacological care for chronic pain already provided in the VHA system. Adverse events will be reported by patients via the IVR system and/or medical records review.

COPES (IVR CBT-CP) and synchronous CBT-CP are minimal risk interventions and CBT-CP and its variants are considered standard of care for chronic pain. COPES (IVR-CBT-CP) participants will be centrally treated at VACHS. Regular meetings will be held between the PI and study staff members who will be delivering the intervention locally from VACHS. Additionally, for the synchronous CBT-CP participants study staff will review participant's electronic health records to identify AEs and UPIRSO.

## 7.2 Methods and Timing for Assessing, Recording, and Analyzing Safety Parameters

Suicide risk assessment.

The interventions in this trial are not believed to increase suicidal ideation, and in fact may be beneficial in improving emotional functioning. However, in the course of baseline or post-treatment and follow-up assessment we may learn information about patient's suicide risk. Participants will complete questionnaire measures via the study IVR system. If they answer any questions in a manner that indicate elevated risk (PHQ-8 score  $\geq 10$ ), they will be automatically asked by the IVR system if they would like to be connected to the Veteran Crisis line. This allows the Veteran to choose to be transferred without hanging up and making another call. We have successfully used this process in prior studies.

During any IVR call (assessment or treatment) participants have the option of connecting to the Veteran Crisis Line. Participant's primary care physician will be informed of any important discoveries made during this study that may affect the patient, their condition, or their willingness to participate in this study. If we discover that the patient is experiencing suicidal thoughts, we will share this with the primary physician immediately (VA patients are assigned to a primary care provider and this provider is noted in their electronic health record). If the participant is receiving care from a mental health provider that person will also be alerted.

Synchronous CBT-CP. VHA Evidence-Based Psychotherapy CBT-CP (referred to as synchronous CBT-CP) is a 10-session intervention containing skills similar to those contained in COPEs. Patients attend weekly, individual, 50-minute treatment sessions with a previously trained CBT-CP therapist. A detailed therapist manual, available on-line, provides pain education, case examples, and session by session guidance on treatment delivery. Therapists in this condition will use clinical judgement and follow VA suicide risk procedures as is required of all VA mental health clinicians. Therapists are required to document suicide risk evaluations and follow-up procedures. Study staff will be able to detect these events when reviewing patient electronic health record data for adverse events. Clinical action for suicide risk evaluation and management identified during synchronous CBT-CP sessions will be managed by local clinicians, not study staff.

